#### 4.4.1.3 SAEs

##### 4.4.1.3.1 Last Vaccination

Last vaccination will be computed using the same methodology as for unsolicited non-serious AEs described in Section 4.4.1.2.2.

##### 4.4.1.3.2 Time of Onset

Time of onset will be computed using the same methodology as for unsolicited non-serious AEs described in Section 4.4.1.2.3.

SAEs will be analyzed throughout the study using the following periods:

- Within 28 days after each/any injection
- During the study (i.e., all SAEs occurred during the study)

An SAE with missing time of onset will be considered to have occurred after the vaccination indicated by the visit number, so will be included in these tables.

Note: SAEs that occurred before vaccination (negative time of onset) will not be included in analysis, but will be listed separately.

Note for SAEs: Elapsed time from last vaccination recorded will be calculated if the SAE occurred within 24 hours of vaccination.

#### **4.4.1.3.3 Duration**

Duration will be computed using the same methodology as for unsolicited non-serious AEs described in Section 4.4.1.2.4 .

#### **4.4.1.4 Other Safety Endpoints**

##### **4.4.1.4.1 Action Taken**

This information will be presented for solicited reaction after each injection. Listing will be also presented separately. No derivation or imputation will be done.

##### **4.4.1.4.2 Seriousness**

This information will be presented for all and related SAE within 28 days post-injection. Listing will be also presented separately. No derivation or imputation will be done.

##### **4.4.1.4.3 Outcome**

This information will be presented for all and related SAE within 28 days post-injection. Listing will be also presented separately. No derivation or imputation will be done.

##### **4.4.1.4.4 Causality**

This information will be summarized as collected. Missing causality (relationship) will be handled as described in Section 5.3.1.2.

#### **4.4.1.4.5 AEs Leading to Study Discontinuation**

A flag is available in the clinical database for all AEs in order to identify AEs leading to discontinuation.

#### **4.4.1.4.6 AEs of Special Interest (AESIs)**

The following serious AESIs (reported as SAEs) will be considered:

- Serious hypersensitivity/allergic reactions occurring in all subjects within 7 days after vaccination
- Serious viscerotropic disease occurring in all subjects within 30 days after vaccination
- Serious neurotropic disease occurring in all subjects within 30 days after vaccination
- Serious dengue disease requiring hospitalization occurring in all subjects at any time during the study

The following non-serious AESI will be considered:

- Hypersensitivity/allergic reactions occurring in all subjects within 7 days after vaccination

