1.3.2 Potential Risks to Subjects

CYD Dengue Vaccine

During the clinical development of dengue vaccine as well as during the Active Phase of the Phase III efficacy studies, no safety concerns after administration of the CYD dengue vaccine emerged from the pooled safety analysis, providing sufficient evidence that the safety profile of the CYD dengue vaccine is acceptable and similar to the safety profile of licensed vaccines in similar population.

Potential unwanted effects include injection site reactions such as erythema, swelling, induration, and pain. General disorders may also be observed such as fever, malaise, asthenia, myalgia and headache. As for any drugs, a risk of allergic reaction cannot be excluded. Vasovagal malaise linked to the injection procedure may be observed in susceptible individuals. Full list of expected adverse events (AEs) can be found in the Investigator's Brochure.

As CYD dengue vaccine has a yellow fever (YF) vaccine backbone, and YF vaccination has been rarely associated with viscerotropic and neurotropic AEs, this risk has to be considered. This theoretical risk linked to viscerotropism and neurotropism is further addressed in the "Guidelines for assessing viscerotropic and neurotropic AE" document. In the previous studies conducted with the CYD dengue vaccine, no confirmed viscerotropic or neurotropic AEs have been observed.

Although an unexplained higher incidence of hospitalization for dengue in year 1 of follow-up among children younger than 9 years was observed in CYD14 efficacy trial, in particular in children from 2 to 5 years old, the combined analysis of efficacy trials up to year 5 post-injection 1 showed a lower risk of hospitalization for dengue among participants who were 9 years of age or older in the vaccine group than among those in the control group. All subjects who were hospitalized due to dengue fully recovered after receiving appropriate supportive treatment (11).

Following a number of supplemental exploratory analyses (see [Section 1.4](#), Rationale for Amendment 1), it was shown that subjects that were never dengue exposed prior to the first CYD dengue vaccine injection have an increased risk of hospitalized or severe disease, as compared to subjects who received the placebo.

Cervarix

Potential risks for subjects receiving Cervarix include fatigue, myalgia, gastrointestinal symptoms, and arthralgia.

All subjects

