9.2.2.2 Safety Endpoints

Cervarix and CYD dengue vaccine safety in each group:

- Occurrence of immediate AEs reported within 30 minutes after each and any injection
- Occurrence of solicited (ie, pre-listed in the subject's DC and CRF) injection site reactions (pain, erythema, and swelling) occurring up to 7 days after each and any injection
- Occurrence of solicited systemic reactions (fever, headache, malaise, myalgia, and asthenia) occurring up to 14 days after each and any injection
- Occurrence of unsolicited AEs occurring up to 28 days after each and any injection
- Occurrence of non-serious AESIs* reported within 7 days following each and any injection
- Occurrence of SAEs, including serious AESIs (with specific time windows according to the type of AESI*) throughout the trial
- Occurrence of hospitalized VCD cases throughout the trial (ie, from D0 through end of the study)

*Hypersensitivity/allergic reactions (serious or not) within 7 days after each CYD dengue vaccine injection, serious viscerotropic disease within 30 days after each CYD dengue vaccine injection, serious neurotropic disease within 30 days after each CYD dengue vaccine injection; serious dengue cases requiring hospitalization will be reported during the entire study.

Depending on the item, these could include: nature (Medical Dictionary for Regulatory Activities [MedDRA] preferred term), time of onset, duration, number of days of occurrence, Grade of

^a All injection site AEs are considered to be related to vaccination and are therefore all *injection site reactions*.

severity, relationship to vaccine, action taken, whether the event/reaction led to early termination from the study, seriousness, or outcome.

Hospitalized suspected dengue case is defined as an acute febrile illness with diagnosis of dengue requiring hospitalization (with bed attribution). In such cases, 1 unplanned acute blood sample (within the first 5 days after fever onset) will be collected for virological confirmation of hospitalized suspected dengue case. A suspected case will be considered VCD if there is a detection of WT dengue virus by dengue NS1 Ag ELISA and/or dengue RT-PCRs (at the GCI or GCI designated laboratory).

Note: Acute blood sample for all hospitalized suspected dengue cases should be collected within the pre-specified timeframe as described above. If this cannot be accomplished, this sample should still be obtained as soon as possible thereafter, for IDMC severity assessment.

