9.2.2.3.5 Adverse Events of Special Interest

The following AESIs will be considered:

Non-Serious AESIs

- Non-serious hypersensitivity/allergic reactions occurring in all subjects within 7 days after vaccination.

Serious AESIs

- Serious hypersensitivity/allergic reactions occurring in all subjects within 7 days after CYD dengue vaccine injection
- Serious viscerotropic^a disease occurring in all subjects within 30 days after vaccination CYD dengue vaccine injection
- Serious neurotropic^a disease occurring in all subjects within 30 days after vaccination CYD dengue vaccine injection
- Serious dengue cases requiring hospitalization^b, occurring in all subjects at any time during the study

^a Specific guidelines will be provided to the Investigator to help in the assessment of AEs that may be indicative of viscerotropic or neurotropic disease (see Guidelines for Assessing Viscerotropic and Neurotropic AE).

^b Meaning hospitalized suspected dengue cases.

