- \*\* A full physical and clinical examination will be performed and documented on each vaccination visit (mandatory before vaccination) and at the Investigator’s discretion if necessary based on the health status of the subject for the other visits.
- †† Concomitant therapy will be collected for Days 0–28 after each injection only
- ‡‡ In healthy female subjects of childbearing potential. Result of urine pregnancy test should be confirmed as negative before vaccination.
- §§ Blood samples planned during vaccination visits will be taken before vaccination
- \*\*\* In such case, 1 unplanned acute blood sample (approximately 3 mL) will be collected for virological confirmation of dengue disease, by NS1 (nonstructural protein 1) antigen test (ELISA), and/or WT dengue RT-PCR
- ††† Interim phone calls will be given 7 days (+8 days of time window) after each injection (PC1: V01 + 7 days, PC2: V02 + 7 days, PC4: V04 + 7 days, PC5: V05 + 7 days, and PC7: V07 + 7 days) and approximately 2 months after blood samples (PC3: M3 or M4, PC6: M9 or M10, and PC8: M15 or M16) during the 6-month period after each vaccination.
- †††† MA will be delivered to subjects who will not receive further CYD dengue vaccine injection but consent to continue their participation in the study.
- §§§§ Solicited injection site reactions will be collected for Days 0–7 after each injection. Solicited systemic reactions will be collected for Days 0–14 after each injection. Unsolicited events will be collected for Days 0–28 after each injection. SAEs will be reported throughout the study and AESIs will be collected in defined time windows according to the type of AESI (hypersensitivity/allergic reactions [serious or not] within 7 days after each CYD dengue vaccine injection, serious viscerotropic disease within 30 days after each CYD dengue vaccine injection, serious neurotropic disease within 30 days after each CYD dengue vaccine injection; serious dengue cases requiring hospitalization [ie, hospitalized suspected dengue case] will be reported during the entire study).
- \*\*\*\* Termination record will be checked either during a planned study visit or a phone call

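### SAP 4.4.1.4.6 opens the serious AESI windows after any vaccination, while SAP Table 3.1 and the protocol tie them to CYD injections; read literally, Group 2 has five windows against three in Group 1

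*SAP*

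**What the plan says.** The derivation rule is SAP 4.4.1.4.6. It lists "Serious viscerotropic disease occurring in all subjects within 30 days after vaccination", a matching item for serious neurotropic disease, and "Serious hypersensitivity/allergic reactions occurring in all subjects within 7 days after vaccination". None of the three says which vaccine opens the window.

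The same SAP defines the windows differently in the footnote to Table 3.1: "serious viscerotropic disease within 30 days after each CYD dengue vaccine injection", the same for neurotropic disease, and "hypersensitivity/allergic reactions [serious or not] within 7 days after each CYD dengue vaccine injection". The protocol agrees with that footnote. The note under the endpoints in 9.2.2.2 reads "Hypersensitivity/allergic reactions (serious or not) within 7 days after each CYD dengue vaccine injection" and ties the two 30-day conditions to CYD as well. Protocol 9.2.2.3.5 also names CYD for all three windowed serious AESIs, although the wording of two of them is garbled.

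Non-serious hypersensitivity is different, because the protocol disagrees with itself. The endpoint bullet in 9.2.2.2 covers non-serious AESIs "reported within 7 days following each and any injection", while the note attached to that bullet limits them to CYD. Protocol 9.2.2.3.5 has "Non-serious hypersensitivity/allergic reactions occurring in all subjects within 7 days after vaccination".

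SAP 5.7, which lists changes to the planned analyses, does not mention the AESI windows. Hospitalized dengue is collected throughout the study, has no post-injection window and is not affected.

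**The concern.** The two schedules have different numbers of vaccination occasions. In Group 1 every occasion includes CYD. In Group 2 two occasions are Cervarix alone, and the first of these comes about 28 days before any CYD dose. A window that opens after any vaccination therefore opens more often in Group 2.

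The protocol explains why viscerotropic and neurotropic disease are watched: "As CYD dengue vaccine has a yellow fever (YF) vaccine backbone". That reason does not apply to a subject who has so far received only Cervarix. A qualifying event in the weeks after her first visit would still be classified as this type of AESI.

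Protocol 1.4 gives safe co-administration as part of the study's main purpose, and the AESIs are the safety events chosen for the live vaccine. If the SAP rule is programmed as it stands, pooled group totals for these events rest on unequal follow-up in the two groups. The rule that assigns an event to its last vaccination (SAP 4.4.1.2.2, applied to SAEs by 4.4.1.3.1) works from the visit number and does not separate Cervarix from CYD, so it does not correct this.

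**Working it through.** **Plan's own figure.** The header of SAP Table 3.1 gives 5 injections per subject. From the schedule in Protocol 5.1.3: 3 CYD + 2 Cervarix = 5 in each group. Reproduced.

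**Occasions.**
- Group 1: V01 (Cervarix + CYD), V04 (Cervarix + CYD), V07 (CYD) = 3, all with CYD.
- Group 2: V01 (Cervarix), V02 (CYD), V04 (Cervarix), V05 (CYD), V07 (CYD) = 5, of which 3 with CYD.
- Without the third CYD dose: 2 and 4.

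**Window lengths.** Day 0 to Day 7 is 8 days; Day 0 to Day 30 is 31 days.

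**Timing assumptions.** 6 months = 182 days; 12 months = 365 days; Visit 2 falls between Day 28 and Day 42 (Protocol 5.1.4); V04 is 182 days after V01; Group 2's second and third CYD doses are 182 and 365 days after Visit 2.

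**Formula.** Risk days = occasions × window length − overlapping days. The 30-day windows overlap only if Visit 2 is earlier than Day 31. With Visit 2 on Day 28, V01 and V02 share Days 28, 29 and 30, and V04 and V05 share three days likewise, 6 days in all.

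**Literal wording of SAP 4.4.1.4.6:**

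| | Group 1 | Group 2 | Ratio |
|---|---|---|---|
| 7-day, full schedule | 3 × 8 = 24 | 5 × 8 = 40 | 1.67 |
| 30-day, full schedule, Visit 2 on Day 28 | 3 × 31 = 93 | 5 × 31 − 6 = 149 | 1.60 |
| 30-day, full schedule, Visit 2 on Day 31 to 42 | 93 | 5 × 31 = 155 | 1.67 |
| 7-day, no dose 3 | 2 × 8 = 16 | 4 × 8 = 32 | 2.0 |
| 30-day, no dose 3 | 2 × 31 = 62 | 118 to 124 | 1.9 to 2.0 |

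Group 2 time before any CYD dose is 8 days of the 7-day window and 28 to 31 days of the 30-day window. Only the V01 window precedes CYD; the V04 window follows the first CYD dose.

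**CYD-tied wording (SAP Table 3.1, Protocol 9.2.2.2).** 24 against 24 and 93 against 93 days; without dose 3, 16 against 16 and 62 against 62. The ratio is 1.00 throughout.

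**Injections inside the windows, full schedule.** This count matters for reactions caused by a vaccine.
- Windows after any vaccination: 5 injections in Group 1 (over 3 occasions) and 5 in Group 2 (over 5 occasions).
- CYD-only windows: still 5 in Group 1, because V01 and V04 also deliver Cervarix, but 3 in Group 2.

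CYD-tied windows therefore balance risk days but not injections. For hypersensitivity, which Cervarix could also cause, a single CYD-only total would count Cervarix reactions in Group 1 and leave them out in Group 2.

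**The case against.** Much of the SAP limits the damage. SAP 4.2 defers the secondary endpoints to Protocol 9.2, and Table 3.1 says AESIs are collected in CYD-tied windows. SAP 5.2.3 analyses safety after each dose by the vaccine actually received, so Cervarix-alone doses can be told apart there. All safety analyses are descriptive. Protocol 1.3.2 reports no confirmed viscerotropic or neurotropic events in earlier CYD studies, so few or none should be expected here. These points stand, and they confine the effect to pooled per-group and any-dose summaries. They do not resolve the conflict, because 4.4.1.4.6 sits among the calculation methods and contradicts another part of the same document.

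On non-serious hypersensitivity, the SAP wording matches the protocol's endpoint bullet and 9.2.2.3.5, and the safety objective covers both vaccines. That also stands: here the conflict is within the protocol.

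A reader might infer that Group 2 would show about 1.67 times the hypersensitivity reactions of Group 1 and so hide an excess from co-administration. The documents do not support that. Both groups receive the same five injections, so if reactions were roughly additive per injection, the literal wording would produce no imbalance. A reader might also infer that any neurological SAE soon after the first Cervarix dose becomes a neurotropic AESI. Protocol 9.2.2.3.5 refers such events to separate assessment guidelines, which are not among the documents, so only events judged to qualify would count.

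**Conclusion.** The point holds for the three windowed serious AESIs. The SAP derivation is wider than the endpoint it implements, and it contradicts the SAP's own procedures table without being listed as a change. Read literally, it gives 5 windows against 3, or 4 against 2 without dose 3. The result is 1.60 to 1.67 times (1.9 to 2.0 times without dose 3) as many risk days in Group 2, including 8 days (7-day windows) or 28 to 31 days (30-day windows) before any CYD dose.

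These ratios rest on the nominal visit timing above. They describe how background events unrelated to either vaccine would accumulate at an equal daily rate in both groups; they do not predict vaccine-caused reactions. No hypothesis test, alpha level or power is touched. What is at risk is misclassification of events after Cervarix alone, and unequal follow-up behind pooled AESI counts.

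**What to change.** 1. In SAP 4.4.1.4.6, for serious hypersensitivity, serious viscerotropic disease and serious neurotropic disease, replace the reference to vaccination with *after each CYD dengue vaccine injection*, as in SAP Table 3.1 and Protocol 9.2.2.2.
2. For non-serious hypersensitivity, reconcile the protocol's endpoint bullet and 9.2.2.3.5 with the CYD-only note in 9.2.2.2. Then carry the agreed definition into both the SAP derivation and Table 3.1.
3. Present hypersensitivity by vaccination occasion and vaccine received (CYD with Cervarix, CYD alone, Cervarix alone), not as one CYD-only total. Serious reactions after Cervarix alone then stay visible beside the AESIs without being labelled as CYD events.

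The cost is a wording change and one extra table breakdown. No new data are needed: SAEs are collected throughout the study, and unsolicited events are collected to Day 28 after every injection.

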### **4.4.2 Immunogenicity**

#### **4.4.2.1 Computed Values for Analysis**

For the computation of GMTs, any titer reported as < the lower limit of quantitation (LLOQ) will be converted to a value of  $\frac{1}{2}$  LLOQ.

While a single approach will be used for GMTs, two different approaches for geometric mean of the titer ratios [GMTR] will be applied:

- For CYD dengue vaccine, < LLOQ will be converted to  $\frac{1}{2}$  LLOQ for a numerator and < LLOQ will be converted to LLOQ for a denominator
- For Cervarix, < LLOQ will be converted to  $\frac{1}{2}$  LLOQ.

#### **4.4.2.2 CYD Dengue vaccine Seropositivity and other thresholds**

Several thresholds of interest will be used to evaluate the immunogenicity of CYD Dengue vaccine.

For each threshold applied on each serotype, the derived indicator will be "Yes" for that serotype if the computed value meets the threshold, otherwise indicator will be "No".

At baseline and 28 days after the 1st and 3rd dose of CYD Dengue vaccine, the thresholds considered are:

---

 A hospitalized subject is any subject admitted to hospital with bed attribution or any healthcare institution and requiring in-patient care.

- Seropositivity: titer  $\geq 10$  (1/dil)
- Distribution rates of titers against each serotype according to the following predefined thresholds (1/dil):  $<10, \geq 10, \geq 20, \geq 30, \geq 40, \geq 60, \geq 80, \geq 100, \geq 120, \geq 140, \geq 160, \geq 180, \geq 200, \geq 220, \geq 240, \geq 260, \geq 280, \geq 300, \geq 320, \geq 340, \geq 360, \geq 400, \geq 640$  and  $\geq 1280$ .

#### **4.4.2.3 CYD Dengue vaccine Seropositivity against at least X serotype(s)**

The criteria below will be computed for each subject and visit as soon as at least one of the four dengue serotype result is different from missing or not-reportable (“NR”) (i.e. coded no result in the serology database):

- Number and percentage of subjects with antibody titer  $\geq 10$  (1/dil) against at least 1, 2, 3, or the 4 serotypes with the parental dengue virus strains.

Titer(s)  $\geq 10$  (1/dil) for at least X serotype(s) with parental dengue virus strains is computed as a Yes/No/Missing variable (note: in the case no titer is available the variable will be missing). If at least X among the 4 serotypes titers meet the threshold then the variable is derived to “Yes”, otherwise if at least one titer is available and does not meet the threshold the variable is derived to “No”. For the percentage calculation, all the subjects with at least one titer available regardless of the serotype will be considered in the denominator.

#### **4.4.2.4 Cervarix Seroconversion**

Seroconversion 28 days after each dose is defined as changing serostatus from seronegative at baseline to seropositive ( $>$  LLOQ of the assay) or  $\geq 4$ -fold rise in Ab titer if seropositive at baseline.

#### **4.4.3 Efficacy**

Not applicable.

#### **4.4.4 Derived Other Variables**

##### **4.4.4.1 Age for Demographics**

The age of a subject in the study is the calendar age.

##### **4.4.4.2 Duration of the Study**

The duration of the study is computed in days as follows:

Latest date of all subjects (termination date, last visit date, date of last contact) – earliest date of all subjects (date of visit V01) +1.

##### **4.4.4.3 Subject Duration**

The duration of a subject participation in the study is computed as follows:

Maximum (Visit dates, Termination date, Follow-up date, Last contact date) – V01 date + 1.

#### 4.4.5 Baseline Dengue status

The dengue serostatus at baseline is defined as the presence of Abs against at least one dengue serotype in the baseline sample (by dengue 50% plaque reduction neutralization test [PRNT50]) in the blood sample collected at V01 for group 1 and at V02 for group 2. The baseline dengue status will be derived for each subject as follows:

- Dengue immune subjects (seropositive) at baseline are defined as those subjects with titers  $\geq 10$  (1/DIL) for at least one serotype with the parental dengue virus strain.
- Dengue non-immune subjects (seronegative) at baseline are defined as those subjects with titers  $< 10$  (1/DIL) (not quantified) for all serotypes with parental dengue virus strains with available and “valid” results (i.e. not coded “NR”) in the serology database.
- Otherwise the baseline status will be classified as undetermined and subjects will have their dengue baseline status derived as non-immune.

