5.1.4 Visit Procedures

All information collected during the study visits must be reported into the source documents. Some of the following information will also be recorded in the case report form (CRF).

Visit 1 (Day 0): Inclusion, Randomization, and Vaccination

The Investigator or designated study personnel will:

- 1) Give the subject's parent/legally acceptable representative information about the trial, obtain written informed consent (ICF and AF when applicable), and give him/her a signed copy.
- 2) Obtain significant medical history about the subject and history of dengue infection.
- 3) Collect demographic data.
- 4) Check concomitant medications and record every reportable medication ongoing at the time of vaccination.
- 5) Check inclusion and exclusion criteria for eligibility.
- 6) Perform a physical examination and record the subject's axillary temperature.
- 7) For subjects of childbearing potential^a, perform a urine pregnancy test.
- 8) Allocate a subject number to the subject.
- 9) Scratch-off the randomization list to obtain the group allocation, and sign it.
- 10) Obtain the first blood sample^b (see [Section 7.1](#) for detailed instructions regarding the handling of blood samples). Blood is to be taken from the limb opposite to the one that will

^a To be considered of non-child-bearing potential, a female must be pre-menarche, surgically sterile, or using an effective method of contraception or abstinence from at least 4 weeks prior to vaccination and until at least 3 weeks after vaccination.

^b It is important to note that, if the attempt(s) to collect blood is (are) unsuccessful, the subject should be given the opportunity for another attempt, even on another day. If ultimately a blood sample cannot be obtained, the reason will be recorded in the CRF. In that case, and if the subject wants to participate in the trial, she will be vaccinated.

be used for vaccination for sequential injection (Group 2), or from the limb opposite to the one that will be used for CYD dengue vaccine injection for concomitant injection (Group 1).

- 11) Inject the first dose of Cervarix to all subjects (from Groups 1 and 2) and the first dose of CYD dengue vaccine to subjects randomized into Group 1 (for concomitant vaccination, the injections are made in opposite deltoid)
- 12) Keep the subject under observation for 30 minutes, and record any immediate AE in the source document.

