9.1 Primary Endpoints and Assessment Methods

9.1.1 Immunogenicity

9.1.1.1 Immunogenicity endpoints

The primary endpoint(s) for the evaluation of immunogenicity are:

Cervarix immunogenicity

- Ab levels (measured by ELISA) against each Cervarix HPV antigen (HPV-16 and HPV-18) 28 days after the last dose of Cervarix in dengue exposed subjects

CYD dengue vaccine immunogenicity

- Neutralizing Ab levels (measured by dengue plaque reduction neutralization test [PRNT₅₀]) against each of the four parental dengue virus serotypes of CYD dengue vaccine (1, 2, 3, 4) 28 days after the last dose of CYD dengue vaccine in dengue exposed subjects

Definition of dengue serostatus

The dengue serostatus at baseline is defined as the presence of Abs against at least one dengue serotype in the baseline sample (by dengue 50% plaque reduction neutralization test [PRNT₅₀]) in the blood sample collected at V01 (BL1) from all subjects. The baseline dengue status variable will be calculated for each subject as follows:

- Dengue immune subjects (dengue exposed) at baseline are defined as those subjects with titers ≥ 10 (1/dil) for at least one serotype with the parental dengue virus strain
- Dengue non-immune subjects (dengue unexposed) at baseline are defined as those subjects with titers < 10 (1/dil) (not quantified) for all serotypes with parental dengue virus strains with available “valid” results (i.e. different from missing or “NR”)

The baseline dengue status will be set to missing when the titer for any serotypes with parental dengue virus is either missing or not quantified. If the titer for all serotypes with parental dengue virus is either missing or not quantified, the dengue status is non-immune.

In case of limited serum volume, the priority will be given to the testing of the dengue serostatus at baseline testing over the other testing (HPV immunogenicity post Cervarix may be not performed if not enough blood volume).

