##### ***Safety***

All analyses will be descriptive; no hypotheses will be tested. Safety will be assessed for all subjects and for immune subjects after each and any dose of Cervarix and CYD Dengue vaccine. Moreover, a complementary analysis will be performed for each dose of CYD dengue vaccine, for each and any group, on non-immune subjects.

As there are differences in the intensity considered for measurable reactions depending on ages of subjects, a complementary analysis will be performed according to the following age groups: 9-11 years and 12 to 14 years.

For the main parameters, 95% CIs of point estimates will be calculated using the normal approximation for quantitative data and the exact binomial distribution (Clopper-Pearson method, quoted by Newcombe) for single proportions.

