### 5.2.1 Full Analysis Set

The Full Analysis Set (FAS) is defined as the subset of subjects who received at least one dose of the study vaccine.

Subjects will be analyzed by baseline dengue status and the vaccine treatment group to which they were randomized.

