#### **5.2.3 Safety Analysis Set**

The SafAS is defined as those subjects who have received at least one dose of the study vaccines. All subjects will have their safety analyzed after each dose according to the vaccine they actually received, and after any dose according to the vaccine received at first dose. The safety data will also be presented separately for dengue immune, non-immune / undetermined subjects.

Safety data recorded for a vaccine received out of the protocol design will be excluded from the analysis (and listed separately).

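### The SAP codes subjects with undetermined baseline dengue status as non-immune, does not list this departure from the protocol, and labels the resulting stratum inconsistently

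*SAP*

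**What the plan says.** SAP 4.4.5 has three steps. A subject with a titer of at least 10 against any serotype is immune. A subject is non-immune if her titers are below 10 for all serotypes "with parental dengue virus strains with available and “valid” results (i.e. not coded “NR”) in the serology database". Everyone else falls under the last bullet: "Otherwise the baseline status will be classified as undetermined and subjects will have their dengue baseline status derived as non-immune".

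The derived status defines the reporting strata:

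- SAP 5.2.1, on the FAS: "Subjects will be analyzed by baseline dengue status and the vaccine treatment group to which they were randomized".
- SAP 5.1.2.2, titers: results by immune, non-immune and all subjects, with no undetermined level.
- SAP 5.1.2.2, safety: "a complementary analysis will be performed for each dose of CYD dengue vaccine, for each and any group, on non-immune subjects".
- SAP 5.2.3, safety: "The safety data will also be presented separately for dengue immune, non-immune / undetermined subjects".

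Protocol 9.1.1.1 handles incomplete results differently: "The baseline dengue status will be set to missing when the titer for any serotypes with parental dengue virus is either missing or not quantified". It continues: "If the titer for all serotypes with parental dengue virus is either missing or not quantified, the dengue status is non-immune".

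SAP 5.7, the section for changes, drops the protocol's separate full analysis set for exposed subjects on the ground that results will be shown by baseline status. It does not mention the handling of undetermined status.

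**The concern.** A subject without a usable baseline result is unknown, not negative. The last bullet of SAP 4.4.5 undoes the validity condition in the bullet before it, so the variable becomes immune versus everyone else under a label that says seronegative.

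Serostatus is the reason for Protocol Amendment 1, and SAP 5.7 relies on the serostatus strata to replace a dedicated analysis set. A reader of the non-immune tables will assume that each subject in them was shown to be negative. If some are in fact immune, their titers after vaccination would raise the stratum's GMT, and their event experience would be averaged into that of true seronegatives. The sections also do not tell a programmer whether undetermined subjects are pooled with the non-immune or shown apart.

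**Working it through.** No figure in the documents depends on this rule, so there is nothing to reproduce. The check traces the rule, then illustrates its size under stated assumptions.

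**1. Can such subjects exist?** Yes. If no blood can be obtained at Visit 1, Protocol 5.1.4 (footnote) says: "In that case, and if the subject wants to participate in the trial, she will be vaccinated". Visit 1 is the dengue baseline draw for Group 1. For Group 2 it is Visit 2, which has no such footnote. SAP 4.4.5 also provides for non-reportable results. No count is given.

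**2. The two rules side by side.**

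| Baseline result | Protocol 9.1.1.1 | SAP 4.4.5 |
|---|---|---|
| All four valid, at least one 10 or more | Immune | Immune |
| All four valid and below 10 | Non-immune | Non-immune |
| Some missing, the rest below 10 | Missing | Non-immune |
| No usable result | Non-immune | Undetermined, then non-immune |

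The third row carries the difference. The SAP's validity condition can be read as needing all four results or only those available; either way this subject ends as non-immune.

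The protocol column needs a caveat, because the same section also uses not quantified to mean below 10. With that meaning the third row would satisfy both protocol sentences, one giving missing and the other non-immune. The first sentence would then also set to missing a subject with one titer of 10 or more and another below 10, against the protocol's own definition of immune. Taking not quantified as no result is less contradictory, and the table uses it.

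**3. Which analyses use the stratum?** PPX and PPC (SAP 5.2.2) exclude subjects classed as non-immune, so undetermined subjects are outside every non-inferiority test. SAP 5.1 allows only descriptive analyses in non-immune subjects.

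**4. Which time points can move?**

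- *Baseline:* any titer of 10 or more would make the subject immune. An undetermined subject's baseline titers are therefore missing (not imputed, SAP 5.3.2) or below 10, and the latter become half the LLOQ, 10/2 = 5, as for every true seronegative. The baseline GMT of the stratum cannot rise.
- *After dose 3:* Protocol 5.1.1 and 7.1.1 limit the third injection and remaining samples to subjects identified as exposed who consent. An undetermined subject should contribute almost nothing.
- *After doses 1 and 2:* all subjects had received two CYD doses before the hold (Protocol 5.1.3), so these titers can be affected, as can safety counts.

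**5. Illustration for titers after doses 1 and 2.** Let f be the share of the reported non-immune stratum that is truly immune, and d the log10 titer gap. The mean log10 titer becomes (1 − f)·m + f·(m + d) = m + f·d, so the GMT is multiplied by 10^(f·d). Both inputs are assumptions.

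| f | d = 0.5 | d = 1.0 | d = 1.5 |
|---|---|---|---|
| 2% | 1.02 | 1.05 | 1.07 |
| 5% | 1.06 | 1.12 | 1.19 |
| 10% | 1.12 | 1.26 | 1.41 |
| 20% | 1.26 | 1.58 | 2.00 |

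The share of undetermined subjects must be at least f, because not all of them need be immune.

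**6. Illustration for event rates.** If misplaced subjects have r times the event rate of true seronegatives, the stratum rate is multiplied by 1 − f·(1 − r). With r = 0.5 (assumed), f = 5% gives 0.975 and f = 20% gives 0.90.

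**The case against.** The strongest reply is that little depends on this. The non-immune outputs are descriptive, no test compares serostatus strata, and the non-inferiority sets are clean. The number affected should be low: Protocol 9.1.1.1 gives baseline dengue testing priority when serum is short, and Protocol 5.1.4 allows a failed Visit 1 draw to be repeated on another day. A subject whose available titers are all below 10, with one result missing, may well be seronegative. SAP 5.2.3 names undetermined subjects for safety, and the protocol itself calls a subject with no usable result non-immune, so the recode is not wholly the SAP's invention. Pooling also groups subjects who share a path after the amendment, and a separate stratum might be too small to summarise.

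Most of this stands and limits the point to a minor one. Three things remain. The slash in SAP 5.2.3 can mean one pooled level or two, and SAP 5.1.2.2 offers neither for titers or by-dose safety. The partly missing case changes from the protocol without being listed. No output is planned that shows the non-immune stratum without undetermined subjects, or how many there are.

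**Conclusion.** The point holds as a minor defect of classification and labelling. A stated rule places subjects of unknown status in a stratum labelled seronegative, and the protocol and two parts of the SAP do not agree on how to treat them. Its reach is the descriptive titers after doses 1 and 2 and the safety counts in that stratum. The size is unknown and probably small; the multipliers above rest on assumed shares and gaps, not on trial figures.

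A reader might infer more, and the documents do not support it:

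- That the primary or secondary non-inferiority tests are contaminated. PPX and PPC exclude these subjects.
- That the trial's comparison of dengue risk by serostatus is compromised. No such comparison is planned; Protocol 1.4 takes that evidence from other trials.
- That non-immune titers are inflated throughout. Baseline cannot be, and after dose 3 almost no such subject should have a titer.
- That the safety tables conceal the mixing. SAP 5.2.3 mentions it, though ambiguously.

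**What to change.** 1. In SAP 4.4.5, keep undetermined as a third category and delete the derivation to non-immune. State whether one missing serotype, with the rest below 10, makes a subject undetermined.
2. Report the number undetermined by arm. Include these subjects in the all-subject tables and leave them out of the immune and non-immune strata. At a minimum, add a non-immune table without them.
3. In SAP 5.2.2, state the PPX and PPC exclusion as not identified as dengue immune at baseline. This matters mainly for PPX, which does not require the third CYD dose and which an undetermined subject could otherwise enter. With this wording neither set changes.
4. Reconcile Protocol 9.1.1.1 with SAP 4.4.5, 5.1.2.2 and 5.2.3, give not quantified one meaning, and list the change in SAP 5.7. SAP 4.4.6 and 4.4.7 use the same fallback for Zika and flavivirus status and could be aligned.

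The cost is some rewording, one more table level and a slightly smaller non-immune stratum. If no subject is undetermined, the results do not change and the report can say so.
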